2.3 Project design

Research design

A randomized controlled trial (RCT) will be conducted in a rural area, following a cross-sectional baseline assessment on situational factors, water quality at the point of collection and point of use, WASH infrastructure, knowledge, attitude and practice as well as health indicators using standardized tools. The follow-up assessment will be conducted 1 year after the intervention (if funding is available a second follow-up assessment 2 years after the intervention might be implemented). One to one matching with the intervention area will be done for the selection of the control area.

The study will comprise of the following intervention schemes

	Baseline scenario	Intervention	Nr of households
Area A	PWS	HHH + S-CHL	375
Area B	PWS	HHH + HWTS	375
Area C	PWS	HHH	375
Area D (Control)	PWS	-	375

PWS is an area with the availability of a piped water supply scheme, that has not yet received the WARM-P training intervention

HHH: household hygiene intervention in accordance with the WARM-P training, but not establishing access to products for household water treatment

HWTS providing access to high quality products for household water treatment and safe storage, including training on adequate product operation and maintenance

S-CHL providing scheme-level chlorination

Conceptual Framework of the Study

The framework of the study is based on the assumption that improved access to safe drinking water together with adequate hygiene and sanitation conditions will improve children's health by reducing diarrhea incidence as well as the incidence of intestinal parasitic infections and therewith improve children's nutritional status.

The framework illustrates that to have a sustainable effect on children's health status a combination of WASH infrastructure improvement and education interventions should be

implemented. The proposed study suggests to assess the improvement of water supply together with strategies to assure drinking water safety and the construction of handwashing stations and latrines. This infrastructural component will be complmented with behavior change interventions targeting drinking water treatment, handwashing and improved hygiene practices. Hence, we hypothesize that a combination of infrastructure and behavior related WASH interventions can influence children's health status. Children's health will further be influenced by the prevailing socio-demographic, socio-cultural, public policy and economic factors, and by the local food security situation.

[figure not shown]

Figure 1: Conceptual Framework of the Study

Assessment indicators

The indicators collected at the household level at the baseline and after the intervention will focus on:

- Water quality at point of collection
- Water quality at the point of consumption,
- Water safety plan management
- Availability, condition and use of WASH infrastructure
- Knowledge, attitude and practice of improved water management and hygiene
- Psychological factors
- Health indicators such as diarrhea and intestinal parasitic infections, particularly the count
 of intestinal helminthic and protozoan eggs. With regard to children's nutritional status, the
 hemoglobin level will be measured for anemia detection; stunting, wasting, thinness, mid
 upper arm circumference will be measured. Clinical examination for detecting wasted
 appearance, dermatitis, pale conjunctiva, xeropthalmia, night blindness, loss of hair
 pigments etc. will be assessed.

Study area

The study will be conducted in Kalikot, Jajarkot, Dailekh, Surkhet and Achham Districts in Western Nepal.

Study Procedure

[figure not shown]

Fig 2: Research Plan

Intervention package

Baseline data collection will take place in the study areas, where households have access to a piped water supply scheme but have not yet received the comprehensive WARM-P WASH intervention.

Data will be collected from 1500 households (375 households per area). Only households providing informed consent will be involved in the study. Intervention activities will start after the completion of baseline data collection in May 2018.

Areas A, B and C will receive household hygiene (HHH), the WARM-P WASH training intervention that aims at improving uptake and use of the following WASH infrastructure elements at household level: the construction of hand-washing stations, dish drying racks, latrines and waste management pits. These infrastructure improvements will be coupled with behavior change training to strengthen improved WASH knowledge, and facilitate consistent practice. Hygiene trainings will be provided during adult literacy classes for caregivers, at schools and during door to door visits. Households complying with the intervention will be provided with a sticker at the door that indicates that the 5 indicators: safe water, better sanitation, personal hygiene, kitchen management and solid waste management have been reached.

The establishment of supply chains for water treatment products will not be part of HHH.

In addition to household level interventions, Area A, B and C will also focus on elements of water safety planning related to the respective water supply scheme, such as system upgrades and regular monitoring visits, while paying attention to the criteria below:

- Area A will equip the water supply schemes with a chlorination system so that chlorinated water is provided at the point of collection.
- Area B will focus on providing access to high quality products for household water treatment (for example high quality ceramic water filters) and safe storage, including training on adequate product operation and maintenance
- Area C will only receive HHH, without providing access to chlorinated water and without providing access to products for water treatment at the household level
- Area D will be the control areas and will not receive any intervention.

The study will be implemented as a collaborative project between Eawag, the Swiss Federal Institute of Aquatic Science and Technology and the NGO, Helvetas Swiss Intercooperation Nepal, Eawag will be responsible for the study design, data collection, data analysis and reporting in accordance with the research design (Step 1 & Step 3). Helvetas Swiss Intercooperation will be responsible for the implementation of activities defined under Step 2.

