Previous collaboration activities with Helvetas in the WARM-P project area revealed significant changes in the hygiene and sanitation condition after a WASH education campaign. Nevertheless, a significant degree of water recontamination between the point of collection and the point of consumption was observed. The proposed study aims at assessing the impact of such an effective training strategy at household level, if the training is combined with an improved water quality intervention.

The impact study will be implemented in Western Nepal in collaboration with Helvetas International Cooperation in the context of their activities on Water Safety Planning in water supply schemes. The evaluation will assess the impact of two interventions aiming at increasing water quality at the point of consumption.

The study is an observational study. Children's caretakers in participating households, will participate twice in a quantitative interview. Health data will be collected from one or two children of participating households. Children's health will be analyzed on the basis of the following indicators: diarrhoea incidence (questionnaire), parasite infection (collection and analysis of stool samples), anthropometric measurements, clinical examination and finger prick tests. The examination of children will be conducted by qualified and trained health personnel. Only households will be involved in the study that have provided written informed consent.

The process of data collection will not cause any health risks to participating humans and therefore can be categorized into Risk category A in accordance with HRO Art.7.

Participating households will not receive any direct compensation for participating in the survey. However, participants will be informed about the outcomes of the study and the results of their personal examination. Those found infected with parasites will be treated in accordance with their infection at recommended doses following standard treatment schemes of WHO.

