2.2 Primary and secondary endpoints

Specific objectives

- 1) To analyze the impact of a water quality and hygiene intervention on:
- Water quality at the point of collection as well as at the point of consumption;
- Availability, condition and use of water, sanitation and hygiene infrastructure; and
- Knowledge, attitude and practice (KAP) of water management, sense of ownership, and hygiene.
- 2) To determine the burden of water-borne diseases (diarrhea and intestinal parasitic infections), malnutrition, nutritional deficiency and anemia among children within the households before and after the intervention.

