3.2 Recruitment, screening and informed consent procedure

Prior to data collection and intervention activities, the selected communities and their leaders will be informed about the goal, purpose and methodology of the study during community meetings. Households in the study site will be selected in accordance with randomized sampling procedures.

An interviewer team of two people will visit the selected households, inform the caregivers of children about the goal, purpose and methodology of the study and hand out the informed consent forms (in Nepali) and request written agreement. If a person is unable to read and write, the information is read out to them and consent will be provided by fingerprints. Households will also be given the contact information of Helvetas-Nepal in case they have any questions about the study. Data will only be collected from agreeing households.

Children displaying signs of defense against participating in the study or against one of the health measurements will not be involved in the study.

Participating households will not receive any direct compensation for participating in the survey.

However, all households in the project areas will benefit from the study by improved management of the drinking water supply, by receiving training on improved hygiene, sanitation and household water treatment and by receiving a facilitated access to products required for water treatment. In control areas, the information on water treatment and access to respective products will be provided after final collection.

Participants will also be informed about the outcomes of the study and the results of their personal examination. Those found infected with parasites will be treated in accordance with their infection at recommended doses following standard treatment schemes of WHO. If signs of infection or anaemia are visible in any of the older children in the participating households, also these older children will be provided with treatment.

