- Hemoglobin (Hb) level will be measured to determine anemia prevalence using Hemocue device.
- Data will be collected from local health centers to identify the recorded prevalence of intestinal parasitic infections, and the prevalence of severe diarrhea of the children in surveyed households.

Data collection tools and techniques

5 qualified interviewers with a minimum schooling qualification of intermediate level and with experience in conducting household surveys will be recruited for data collection. Each interviewer will be accompanied by a data collection assistant. It is assumed that an interviewer-team of 2 people will cover 6 households per day; 5 interviewer teams of 2 people therefore will collect data from 30 households per day (household interviews, collection of water samples, collection of stool samples and measurement of health indicators such as anthropometry, hemoglobin). Time required to conduct the interview, collect samples and measure health data shall not exceed 1.5 hours per household per survey. The period allocated to collect data for one panel (baseline/ final survey) is 3 months.

One lab assistant and one health assistant will supervise stool, blood collection and physical examination. The stools will be collected in labeled plastic cups and will be preserved. The samples will be processed for testing at the hospital. Parasitological examination of the feces will be conducted according to operating procedures defined by WHO. Random reprocessing of 5% of the stool samples will be performed for accuracy purpose. Presence of any parasitic infection will be defined by positive laboratory results for intestinal parasites. All the surveyed children with parasitic infections will be treated. Pre-testing of the data collection tools will be done and the instruments will be pilot tested in the area similar to the project area.

Timeline

		2018									2019												2020					
Activities	1	2	3	4	5	6	7	8	9	10	11	12	1	2	3	4	5	6	7	8	9	10	11	12	1	2	3	4
Health Impact Study Nepal																												
Study preparation, development study tools																												
Baseline Data Collection																												
Intervention Helvetas																												
Data Collection																												
Data Analysis																												
Paper Preparation																												
Information Dissemination																												

Expected biases

We do not expect any biases

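### The protocol calls the study both a randomised trial and an observational study, selects the control area by matching, and describes no random allocation to Areas A to D

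*Protocol*

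**What the plan says.** Three statements in the Protocol bear on the type of design:

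- Section 2.3 (Research design): "A randomized controlled trial (RCT) will be conducted in a rural area".
- The same paragraph of Section 2.3: "One to one matching with the intervention area will be done for the selection of the control area".
- Section 1: "The study is an observational study".

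The random step that the procedures describe is in Section 3.2: "Households in the study site will be selected in accordance with randomized sampling procedures".

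The interventions are delivered to areas or water schemes, not to single households. Section 2.3 says "Area A will equip the water supply schemes with a chlorination system so that chlorinated water is provided at the point of collection" and, for the comparator, "Area D will be the control areas and will not receive any intervention". Each of the four arms has 375 households. The number of schemes per arm is not given.

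The conceptual framework in Section 2.3 accepts that socio-demographic, cultural, policy and economic conditions and local food security affect child health. Section 3.3 (Expected biases) nevertheless says that none are expected.

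Objective 2 in Section 2.2 concerns the burden of disease "among children within the households before and after the intervention", and Section 3.3 adds "All the surveyed children with parasitic infections will be treated". Section 6.1 makes clear that this treatment covers intervention and control areas alike.

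Section 4.1 lists chi-squared and Fisher tests, t tests or ANOVA, repeated-measures regression and logistic regression on repeated outcomes per child.

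**The concern.** Whether a comparison is randomised decides what a difference between arms can mean. If schemes were allocated at random, an imbalance between arms is chance and the analysis can quantify it. If the intervention areas were fixed first and a control area was then found to match, any remaining difference between areas is confounding, and a p-value does not allow for it.

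The Protocol claims the first while describing something closer to the second. A report that follows Section 2.3 could present differences in wealth, food security or local policy as randomised effects of chlorination, household water treatment or hygiene training. Declaring that no bias is expected removes the prompt to look for such differences.

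A second risk is narrower. Because Objective 2 is worded as before versus after, a change within one arm could be read as an intervention effect, although infected children are treated in every arm between the two surveys.

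**Working it through.** The main point rests on text, so the relevant places are set side by side first.

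| Question | What the Protocol gives | Where |
|---|---|---|
| Design label | Randomised controlled trial | 2.3 |
| Design label | Observational | 1 |
| Origin of the control | Selected by matching to the intervention area | 2.3 |
| Random step described | Sampling of households | 3.2 |
| Allocation of areas or schemes to A to D | Not described in the readable text | – |
| Unit treated | Area or water scheme | 2.3 |
| Area-level influences on outcome | Acknowledged | 2.3 |
| Biases | None expected | 3.3 |
| Regulation listed | Ordinance for research other than clinical trials | 9, item 20 |

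The two labels cannot both hold. Random sampling makes the surveyed households representative of their area; it does not decide which area gets which intervention. Matching used to select a control implies that the intervention area is already known.

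**Illustration of size.** The Protocol has no figure to reproduce here. The area differences and intraclass correlations (ICCs) below are assumptions.

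1. Analysed households per arm: 375 × (1 − 0.07) = 348.75, taken as 349 (375 and 7% from Section 4.1).
2. Standard error of a difference between two arms, in SD units: √(2/349) = 0.0757.
3. With no true effect and a persistent, uncorrected area difference b, the chance of a two-sided p below 0.05 is Φ(b/0.0757 − 1.96) + Φ(−b/0.0757 − 1.96).

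| Assumed b (SD) | b / 0.0757 | Chance of p < 0.05 |
|---|---|---|
| 0.05 | 0.66 | about 10% |
| 0.10 | 1.32 | about 26% |
| 0.20 | 2.64 | about 75% |

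4. If each arm were a single area (not stated), area effects would act as between-cluster variation. The design effect is 1 + 348 × ICC, and the naive two-sided error is 2 × [1 − Φ(1.96/√(design effect))].

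| Assumed ICC | Design effect | Naive type I error |
|---|---|---|
| 0.001 | 1.35 | about 9% |
| 0.01 | 4.48 | about 35% |
| 0.05 | 18.4 | about 65% |

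**How far baseline adjustment helps.** With equal variances, regression on the child's own baseline subtracts the correlation times the baseline gap. At the correlation of 0.1 used in Section 4.1, an assumed gap of 0.10 SD is corrected by 0.1 × 0.10 = 0.01 SD, which leaves 0.09 SD if the gap persists. A difference in differences subtracts the whole 0.10 SD, provided the areas would otherwise have moved in parallel. Its variance is 2 × (1 − 0.1) = 1.8 times that of a follow-up-only comparison. Neither removes unmeasured differences in trend between areas.

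**The case against.** The strongest reply is that matching and randomisation are compatible: schemes can be grouped into matched sets and then drawn at random. Figure 2 (the research plan) is not shown, and allocation detail may sit there. This stands as a limit. The documents do not prove that allocation was non-random; they leave it undescribed and contradict themselves on the label. A figure would not remove the conflict between Sections 1 and 2.3.

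It can also be said that Section 4.1 already plans repeated-measures models and that exact covariates belong in an analysis plan. That is fair: the tools for adjustment are there, and missing covariate detail is not the finding. The finding is the contradictory basis for the arm contrasts.

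Two stronger readings may tempt a reader, and the documents support neither:

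- *One-to-one matching is impossible because 3 × 375 = 1125 intervention households face 375 controls.* Each arm has 375 households, so each of A, B and C can be matched 1:1 to D. The total of 1125 to 375 is not a matching ratio, and the wording should not be changed to 3:1.
- *Treating infected children biases the arm comparison.* Treatment applies in all arms, and a shift common to all does not by itself bias a between-arm contrast. Section 1 already frames impact against the control area. The treatment affects only the reading of change within an arm.

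**Conclusion.** The point holds as a contradiction in the Protocol. The study is labelled randomised in Section 2.3 and observational in Section 1, its control is selected by matching, and no readable text describes random allocation to A to D. Until this is reconciled, the arm contrasts have no stated basis for a randomised causal claim, and the no-bias statement conflicts with the area-level influences that the Protocol itself names.

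The size cannot be read from the documents. Under the assumptions above, a modest uncorrected area difference of 0.10 SD would raise the false-positive rate from 5% to about 26%. The clustering figures apply only if each arm is one area, which is not stated. Baseline adjustment is needed but is not sufficient: it cannot remove unmeasured area differences or stand in for replicated schemes.

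**What to change.** Reconcile Sections 1 and 2.3 by one of two routes:

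- **(a) Randomise.** If enough schemes exist, group eligible schemes into matched sets of four and draw A to D at random within each set before intervention activities start. State the unit, the number of sets and the method of the draw. As a floor for feasibility, a randomisation test of one pair of arms across k sets cannot give a two-sided p below 2/2^k: 0.0625 for k = 5 and 0.031 for k = 6.
- **(b) Relabel.** Replace the RCT label with non-randomised controlled before-after study, state how each area was chosen, and limit the causal claims accordingly.

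In both cases:

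- Define each effect as a between-arm contrast at follow-up, or a difference in differences, adjusted for the baseline outcome, measured confounders and the matching set. Name the choice in advance; under (b) the two can differ, as shown above.
- Base inference on schemes or areas as clusters.
- State that before-after change within an arm is descriptive.
- Replace the no-bias statement with one on possible area-level confounding.

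**Cost.** Route (b) is wording plus baseline data already planned, at the price of a weaker causal claim. Route (a) needs a draw, the implementing partner's agreement and a sufficient number of schemes, which the Protocol does not give. Under both, intervals widen once clustering is counted, and under Section 5.5 a substantial change needs ethics approval before it is implemented. Route (b) needs no extra participants; neither does (a) if the existing schemes suffice.

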3 PROJECT POPULATION AND STUDY PROCEDURES

3.1 Project population, inclusion and exclusion criteria

Data will be collected from 1500 households (375 households per area). Only households with at least one child in the age between 6 months to 10 years will be involved in the study. If a participating household has more than one child, the health of the youngest child will be examined as the vulnerability of young children for diarrhoeal infections is highest.

3.2 Recruitment, screening and informed consent procedure

Prior to data collection and intervention activities, the selected communities and their leaders will be informed about the goal, purpose and methodology of the study during community meetings. Households in the study site will be selected in accordance with randomized sampling procedures.

An interviewer team of two people will visit the selected households, inform the caregivers of children about the goal, purpose and methodology of the study and hand out the informed consent forms (in Nepali) and request written agreement. If a person is unable to read and write, the information is read out to them and consent will be provided by fingerprints. Households will also be given the contact information of Helvetas-Nepal in case they have any questions about the study. Data will only be collected from agreeing households.

Children displaying signs of defense against participating in the study or against one of the health measurements will not be involved in the study.

Participating households will not receive any direct compensation for participating in the survey.

However, all households in the project areas will benefit from the study by improved management of the drinking water supply, by receiving training on improved hygiene, sanitation and household water treatment and by receiving a facilitated access to products required for water treatment. In control areas, the information on water treatment and access to respective products will be provided after final collection.

Participants will also be informed about the outcomes of the study and the results of their personal examination. Those found infected with parasites will be treated in accordance with their infection at recommended doses following standard treatment schemes of WHO. If signs of infection or anaemia are visible in any of the older children in the participating households, also these older children will be provided with treatment.

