3.3 Study procedures

Methods and approaches for objective 1: Water quality at the point of collection as well as at the point of consumption will be analyzed by field based methods using membrane filtration and the quantification of fecal indicators organisms such as E.coli and total coliforms. Water quality measurements will also include detection of free residual chlorine levels, turbidity, pH, conductivity, and nitrate.

Household information on WASH infrastructure, knowledge, attitude and practices will be gathered by a combination of qualitative (structured observations) and quantitative methods involving structured household interviews using tablets with digital questionnaires. Household survey questionnaires will include specific questions assessing KAP of WASH and health including household information, access to water, WASH know how, practice, attitude, self-efficacy, planning, behaviors, health status and risk awareness, social norms, perception of the water system, information on WASH promotion, market information, wealth index, and observation through interviewers.

Methods and approaches for objective 2: To determine the burden of water-borne diseases and the health impact of the interventions, the following indicators will be assessed by a combination of qualitative and quantitative methods:

- Diarrhea: baseline diarrhea incidence will be assessed by asking households about diarrhea
 prevalence during past 2 weeks prior to data collection. Households participating in the study
 will be requested to fill out a diary on diarrhea prevalence between baseline and of follow-up
 assessment.
- Intestinal parasitic infections: stool analysis will be done for determining the prevalence and type of intestinal parasites. Kato-Katz, formal-ether and wet mount methods will be used for soil-transmitted helminthes and intestinal protozoa respectively.

- Nutritional status: Anthropometric measurements for age will be used to account for normal growth and development of children. Children with z-scores for weight-for-height, weight-forage, and height-for-age <2 standard deviations of the median of the WHO reference population will be considered wasted, underweight and stunted respectively.
- Nutritional deficiency: Physical examination and clinical observation including dermatosis, pale conjunctiva etc. will be conducted by a trained health care professional. (food security will be assessed through questions in the interview)

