4 STATISTICS AND METHODOLOGY

4.1. Statistical analysis plan

Descriptive statistics will be calculated to describe the characteristics of the population and the status of WASH indicators. Frequencies and percentage will be computed for categorical variables while means and standard deviations will be calculated for continuous variables. Positive cases identified during health screening will allow estimating point prevalence. Pearson's chi squared and Fisher's exact test will be applied for finding the association with the prevalence of diarrhea, intestinal parasites (single, multiple), nutritional disorders and risk factors. Means will be compared by student's t test or ANOVA. Repeated measures multiple regressions will be used to find an association between binary or continuous outcomes and adjacent variables. Logistic regression analysis will be used to compare repeated binary health outcomes per child in multiple groups. Univariate association between two binary variables will be assessed through 2X2 tables. Categorical variables will be compared using design based chi-square analysis. In all analyses, a p- value (threshold of significance) <0.05 will be considered statistically significant.

Sample size and power calculations using G*Power 3.1 revealed a sample size of 350 households in each group to detect a small effect between 4 groups with a correlation of 0.1 among repeated measures with 80% power and a one-tailed alpha of 0.05 (Erdfelder *et al.* 1996). A sample size of 300 households will be required to detect a small to medium effect in Cohen's f2 at one-tailed alpha of 0.05 and a statistical power of 95% with multiple linear regression and 15 predictor variables (Faul et al., 2009).

We will sample 375 households per study area, which will have the advantage to better balance potential design effects. The same sampling plan will be used during the follow up study in both beneficiary and control areas. In addition, a drop-out rate of 7% is being considered.

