6.3 Rationale for the inclusion of vulnerable participants

Children will be involved in the study because they are particularly sensitive to and affected by diarrhoea related morbidity and mortality. A study hypothesis therefore is, that particularly children below the age of 5 will experience the greatest health benefits from an intervention focusing on water safety and improved hygiene and health. Their health related indicators need to be assessed to confirm the hypothesis and evaluate the impact of the study on children's health. The collection of health data will not expose children to any risk.

Children's caretakers will be well informed about the purpose of the study and the methodology. Data will only be collected in households where children's caretakers have provided written informed consent. Participating children will be orally informed about the study and the purpose of the health measurements. They will be gently informed about the process of measurements before starting the examination.

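### Section 3.2, read literally, drops a child from the whole study for resisting one measurement, losing child outcomes that do not depend on it

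*Protocol*

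**What the plan says.** The rule stands in section 3.2 (recruitment, screening and informed consent): "Children displaying signs of defense against participating in the study or against one of the health measurements will not be involved in the study". It joins two situations with one consequence: objecting to the study, and objecting to a single procedure. No other section lets a child in the second situation keep the remaining data.

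The children concerned are defined in section 3.1: "Only households with at least one child in the age between 6 months to 10 years will be involved in the study". Where there are several children, "the health of the youngest child will be examined as the vulnerability of young children for diarrhoeal infections is highest". Section 6.3 adds the hypothesis that "particularly children below the age of 5 will experience the greatest health benefits".

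Section 3.3 lists the child outcomes. Some need nothing from the child: "baseline diarrhea incidence will be assessed by asking households about diarrhea", followed by a household diary, and "Data will be collected from local health centers to identify the recorded prevalence of intestinal parasitic infections" (severe diarrhoea is also taken from those records). The others are stool analysis, anthropometry, clinical examination and haemoglobin, the last by finger prick.

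On losses, section 3.4 attributes expected drop-out to relocation and mobility of households, and section 4.1 says that "a drop-out rate of 7% is being considered". Section 4.1 gives a requirement of 350 households per group for the repeated-measures comparison; section 4.2 gives 300 per area. Both lead to 375 sampled per area. Under its heading on biases, section 3.3 expects none.

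**The concern.** Respecting a child's dissent is a proper safeguard. The difficulty is how far the sentence carries it: from the resisted procedure to every outcome on that child. If a child accepts weighing, measuring and stool collection but not the finger prick, only haemoglobin needs to be missing. The sentence makes everything on the child missing.

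Three things are at stake.

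- **Number of children.** The loss is not evidently covered by the drop-out allowance, whose stated causes are relocation and mobility.
- **Who remains.** The index child is the youngest, from 6 months of age. If resistance is commoner at younger ages, the rule removes relatively more of the group in which the protocol expects the largest effect.
- **When it acts.** The sentence is not expressly limited to baseline, and the health measurements are repeated at follow-up. Exclusions made after the interventions have started could differ between areas in a way that recruitment-stage exclusions would not.

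**Working it through.** **Inputs from the protocol:** 375 households per area; 7% drop-out; requirement 350 (section 4.1) or 300 (section 4.2). **Not in the protocol, assumed here:** the proportion r of children resisting at least one measurement; its variation with age; and that resisting children are not replaced.

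**1. The plan's own figure.** Adding 7% to 350 gives 350 × 1.07 = 374.5, so 375. Dividing by the retained fraction gives 350 / 0.93 = 376.3, so 377. The stated 375 is therefore reproduced, to within two households, as 350 plus 7% drop-out. In the other direction, 375 × 0.93 = 348.75, about 349. Against 350 nothing is left over for any other loss. Against 300 the room is 1 − 300/348.75 = 14%.

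**2. Children per area with any child outcome under the rule as written:** n = 375 × 0.93 × (1 − r).

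| Assumed r | n under the rule | Sample needed to keep 350: 350 / (0.93 × (1 − r)) |
|---|---|---|
| 0% | 349 | 377 |
| 5% | 331 | 397 |
| 10% | 314 | 419 |
| 20% | 279 | 471 |

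If only the resisted measurement were set missing, about 349 children would remain in follow-up and only the refused item would have a smaller denominator.

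**3. Why r may exceed the refusal rate of any single measurement.** The trigger is resistance to any one of several procedures. With four measurements and independent refusal at rate p each (both assumed), the excluded share is 1 − (1 − p)^4: 7.8% at p = 2% and 18.5% at p = 5%. Measurement-level coding would cost each outcome only p.

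**4. Age mix.** Suppose 60% of index children are under 5 (assumed).

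- Resistance 20% under 5 and 5% above: 0.60 × 0.80 = 0.48 and 0.40 × 0.95 = 0.38 remain. Excluded: 1 − 0.86 = 14%. Under-5 share: 0.48 / 0.86 = 55.8%.
- Resistance 10% and 2%: 0.54 and 0.392 remain. Under-5 share: 0.54 / 0.932 = 57.9%.
- Equal resistance: the share stays at 60%.

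The shift is therefore two to four percentage points under these gradients, and nil without a gradient.

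**5. Scope and timing, from the text.** The subject of the sentence is children, not households. Eligibility and consent are set at household level, and water quality, infrastructure and knowledge are household data. The sentence stands in the recruitment section, before any intervention (section 2.3 starts the interventions after baseline data collection). It neither restricts itself to recruitment nor says what happens to a child who first resists at follow-up.

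**The case against.** The best defence is that this is an enrolment and assent rule. It stands directly after the consent procedure, and losses between surveys have their own section (3.4). If resisting children are screened out and sampling continues until 375 households per area are reached, the sample size does not suffer, and exclusions made before the interventions cannot be a consequence of them. Stopping at the first sign of resistance also spares a distressed child the rest of the visit. This is a fair reading, and the text does not rule it out. It does not rule out the other reading either, and even at recruitment the rule turns away children whose remaining data could have been used.

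A second objection concerns size. Take a standardised difference of 0.2 between two areas (assumed, as the protocol says only that the effect is small) and the protocol's one-tailed 5% level. Power Φ(0.2 × √(n/2) − 1.645) is then about 84%, 82%, 81% and 76% at r = 0, 5, 10 and 20%. Up to 10% resistance the planned 80% is kept on this simple calculation, and the 300 of section 4.2 is still met. This stands: at modest rates the loss of power is small.

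Three stronger readings may tempt a reader, and the protocol does not support them. First, that household water quality is lost as well: the sentence removes the child and is silent on the household. Second, that the rule certainly operates at follow-up: the text leaves this open. Third, that the youngest are shown to be removed selectively: no rate of resistance is given, overall or by age.

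**Conclusion.** The point holds as a defect of wording with a practical cost. As written, the rule is all-or-nothing for the child, and it gives up outcomes that do not depend on the resisted measurement. Its size cannot be fixed from the protocol. Without replacement, and at assumed resistance of 5% to 20%, the loss is about 17 to 70 children per area (348.75 × 0.05 to 348.75 × 0.20). No margin remains against 350, and 14% remains against 300.

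Thinning of the under-5 group depends on an assumed age gradient and is modest in the cases worked. At recruitment it would affect generalisability rather than the comparison between areas. Bias in that comparison would arise only if the rule were also used at follow-up and bore unequally on the areas, or were applied unevenly across areas at recruitment. The protocol does not settle when it applies. Nothing here makes the trial invalid; the correction is cheap and worth making.

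**What to change.** Split the sentence in section 3.2 into two rules. A child who objects to taking part is not enrolled. A child who resists one measurement, at baseline or at follow-up, is not given that measurement; it is recorded as refused, and all other consented data on the child and the household are kept (diarrhoea report and diary, stool, records, accepted measurements, interview, water samples). State that the household remains in the study, and report refusals by measurement, area and age.

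The cost is one reworded sentence, a refused code in the tablet form, and ethics approval of the wording under section 5.5. The drawback is that denominators will differ between outcomes and must be shown for each.
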